Aim 1: Evaluate to what extent a multifaceted intervention (ISOT) enhances prescription opioid safety. For Aim 1, we use 8.9 as an estimated standard deviation (SD) for change in COMM score from baseline to 12 months.⁹⁵ This SD estimate is based on SD's in prior intervention research.³³ For each group, an estimated SD for change was obtained using the two SD's and a within-subject intraclass correlation coefficient of 0.5. Averaging the corresponding variances leads to an estimated variance of 78 (SD=8.9). Power calculations were performed based on 28 or 32 (we may recruit as many as 40 PCPs, but do not anticipate that many will consent to participate) clinicians per intervention group and 4 or 5 patients per clinician. Table 1 displays differences in mean COMM change that can be detected under various values for the intraclass correlation coefficient. Our targeted sample size is 32 PCPs per group and an average of 5 patients per PCP. With a loss of 4 PCPs per group and 1 patient per PCP, we have power to detect small differences (able to detect $< \frac{1}{2}$ SD change) in COMM score. For Aim 1, we plan to conduct analyses for self-report data (COMM), clinical interviews to assess current substance use disorders (SCID), and results from research-administered UDTs. With n=320, 28-32 PCPs per group, and 4-5 patients per PCP, we have statistical power greater than 80% to detect differences in percentages between groups of about 20% for binary outcomes from the SCID and UDT (see Table 2 below for similar calculations for Aim 2).

Table 1. Mean differences in COMM change from baseline to 12 months (80% power, $\alpha=0.05$).

Intra-class correlation	Mean detectable difference in COMM change, n=4 patients per clinician, 28 clinicians per intervention	Mean detectable difference in COMM change, n=4 patients per clinician, 32 clinicians per intervention	Mean detectable difference in COMM change, n=5 patients per clinician, 28 clinicians per intervention	Mean detectable difference in COMM change, n=5 patients per clinician, 32 clinicians per intervention
0	3.4	3.2	3.0	2.8
0.02	3.5	3.3	3.2	2.9
0.04	3.6	3.4	3.3	3.1
0.10	3.9	3.6	3.6	3.4

Analyses for Aim 1: For comparison of mean COMM change between groups, we will use mixed longitudinal models with a random effect for PCP and patient, to allow for correlation between

observations on different patients of the same PCP and for repeat observations on the same patient. Transformations of the outcome will be applied to meet distributional assumptions. In linear mixed models, we will include baseline measures of patient age, sex, depressive symptoms, history of SUD, and pain severity as covariates. We will also adjust for baseline COMM score and the stratification variables: PCP training type (MD/DO vs NP or PA) and proportion of clinician panel prescribed opioids (high vs low). In addition to testing formal hypotheses, we will report 95% confidence intervals for the differences in mean outcomes between groups at 6 and 12 months. For comparing the percentages classified as abusing opioids at any time during follow-up (combining information from 6 and 12 months) based on SCID and UDT, we will use generalized-linear mixed models (or GEE as needed) to incorporate correlation between patients of the same PCP. We will adjust for baseline measures of the outcome along with the covariates listed above. We will report group comparisons on all three primary outcomes (COMM, SCID, and UDT). Assuming 15% of the sample has current SUD (consistent with other research), we will not conduct interaction analyses, but will present descriptive information for each outcome (COMM, SCID, UDT) on treatment outcomes by SUD status.

Data on opioid-related adverse events will be obtained from the medical record and participant self-report. We will collect data on opioid overdoses, falls, motor vehicle accidents, and ER visits related to pain. Descriptive information on opioid-related events will be provided for each group (numbers and percentages of participants with each event). Because the number of adverse events is expected to be small, we will use Fisher's Exact test to compare adverse event percentages between groups. We will compare both percentages for each individual type of event as well as percentages of individuals experiencing any adverse event between groups.

Aim 2: Assess to what extent assignment to ISOT impacts pain treatment-related processes of care. The power for comparing the percentage of patients receiving at least one UDT (Table 2) during the follow-up period assumes that 40% of patients in the control group will receive a follow-up UDT.²¹ This is based on prior research in which 26% of patients had a UDT and our expectation that the percentage will be higher in the control group after clinicians participate in the workshop. We hypothesize that clinicians randomized to ISOT will have much higher rates of administering UDTs. Regarding checks to state PDMPs, currently 3-5% of VAPORHCS patients receive a query. The ISOT protocol prompts the clinician to conduct PDMP queries and we expect dramatic differences in percentages between the two intervention groups. We have 80% power to detect differences of 17-21% on binary outcomes. Here we expect differences to be much greater.

Table 2. Urine drug test percentage in the intervention group that can be detected (80% power, $\alpha=0.05$) *compared to a usual care percentage of 40%*.

Intra-class correlation	Urine drug test % that can be detected in the intervention group, n=4 patients per clinician, 28 clinicians per intervention	Urine drug test % that can be detected in the intervention group, n=4 patients per clinician, 32 clinicians per intervention	Urine drug test % that can be detected in the intervention group, n=5 patients per clinician, 28 clinicians per intervention	Urine drug test % test that can be detected in the intervention group, n=5 patients per clinician, 32 clinicians per intervention
0	59%	57%	57%	56%
0.02	59%	58%	57%	56%
0.04	60%	58%	58%	57%
0.10	61%	60%	60%	58%

Aim 2: Assess to what extent assignment to ISOT impacts the quality of the clinician-patient relationship. Using estimated standard deviations of 14.2 for the Trust in Physician Scale⁸⁴ and

28.9 for the Participatory Decision Making Style,⁸⁶ we have 80% power at level 0.05 to detect mean differences between groups at 12 months of 4.7 to 5.6 and 9.6 to 11.3, respectively, using 28 to 32 clinicians per intervention group, 4 to 5 patients per clinician, and assuming an intraclass correlation of 0.02. If we focus on change from baseline, the power for comparisons at each follow-up time-point would be greater, provided the correlations between baseline and follow-up are greater than 0.5.

Clinicians will also be queried about perceived barriers and potential effectiveness of screening for prescription opioid abuse. With 32 pairs of clinicians and intra-class correlations of 0 to 0.1, we would have 80% power to detect differences of 0.50 to 0.53 SDs in mean summary scores between intervention groups.

Analyses for Aim 2: We will use GEE methods to compare between intervention groups the average numbers of clinical care documentations, UDT's, and queries to state prescription drug monitoring programs while adjusting for the baseline covariates (age, gender, depressive symptoms, history of SUD, and pain intensity) and the stratification variables. For patient level data, the approach for analysis of Aim 2 outcomes will be the same as that for Aim 1, using mixed models and/or GEE for comparisons, while adjusting for baseline covariates (age, sex, depressive symptoms, history of SUD, and pain severity), baseline measure of the outcome, and stratification variables (training type, proportion of panel prescribed opioids). Analyses will be conducted for scores on the Trust in Physician scale and Participatory Decision Making Style.

For clinician and PACT nurse data on barriers to use of UDTs, we will report descriptive information for each of the 10 questions. For each group and question, we will report the percentage of clinicians with scores at each of the five levels at baseline and follow-up, as well as the corresponding descriptive change information in follow-up scores. We will report the mean (and SD, min, max) of change for each question. We will obtain an overall survey score, by averaging the 10 question scores for each clinician and report the mean (and SD, min, max) survey score for each group at baseline and follow-up, along with the mean change (and SD, min, max) in survey score. We will use linear mixed models on the change scores to compare groups, while adjusting for clinician age, clinician training type, sex, panel size, summary survey score at baseline, and stratification variables. We will include a random pair effect to allow for correlation between the PCP and PACT nurse within each pair. P-values and 95% confidence intervals for the differences between groups in change scores will be provided. Similar analyses will be conducted for examining survey data on clinician satisfaction with ISOT.

Aim 3: Explore to what extent ISOT is associated with changes in pain intensity, function, quality of life, and depressive symptoms. Our goal is to improve opioid safety while not adversely impacting pain or quality of life. Power calculations were performed for pain intensity based on 28 or 32 clinicians per intervention group and 4-5 patients per clinician, using data indicating a baseline mean pain intensity score of 66 and estimated SD of change from baseline of 13.1.⁴⁸ Here we are interested in tests of non-inferiority; specifically we aim to show that the reduction in mean pain intensity for the ISOT group is no more than one-half standard deviation less than that for the control group. Considering the same set of conditions given in Tables 1-2, the worst case scenario (n=4 patients per clinician, n=28 clinicians per intervention and intraclass correlation of 0.10), results in power greater than 80% at level 0.025 for testing non-inferiority of pain intensity if the true mean change for ISOT patients is not more than 0.9 units less than the control group. Similarly for change in pain-related function, quality of life, and depressive symptoms, we considered a one-half SD difference in change to be the appropriate non-inferiority limit.^{96,97} We have power greater than 80% at level 0.025 for testing non-inferiority, if the mean change in function, quality of life, and depressive symptoms for the ISOT group are no more than 1.8, 0.9, and 0.4 units, respectively, less than those for the control group. These are based on estimated SD's for change assuming a 0.5 correlation between baseline and follow-

up.

Analyses for Aim 3: For analysis of pain intensity, we hypothesize that the mean reduction in pain (measured by CPG pain intensity scale) for patients randomized to ISOT is no more than 6.6 points less than the control. Although we will conduct a formal test of this non-inferiority hypothesis, our primary goal is to estimate the difference in mean reductions between the groups at each time-point, anticipating that the differences will be small. Construction of a lower bound (97.5%) corresponds specifically to the non-inferiority hypothesis of interest, but we will also obtain the corresponding (97.5%) upper bound. As with comparison of continuous outcomes for the other aims, mixed models will be used for hypothesis testing and confidence interval construction and we will adjust for covariates measured at baseline (patient age, sex, depressive symptoms, history of SUD, and pain severity), stratification variables, and baseline score. We will use the same approach to examine potential differences between groups on measures of pain-related function, quality of life, and depressive symptoms.

REFERENCES

1. Kuehn BM. Opioid prescriptions soar: Increase in legitimate use as well as abuse. *JAMA*. 2007;297:249-251.

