
assigned to work with must also participate. **Patients:** All patients enrolled in primary care clinics will be potentially eligible.

Inclusion Criteria: Participants must be enrolled in primary care at the VAPORHCS and be receiving chronic opioid therapy for chronic pain unrelated to a life-limiting disease. Chronic opioid therapy is defined as receiving an opioid prescription in three consecutive months or six prescriptions in the last year with a current prescription.²⁰ The only other inclusion criterion is the ability to read and write in English. **Exclusion Criteria:** Age younger than 18 years, opioid therapy for palliative or end-of-life care, current enrollment in an opioid substitution program, or lack of telephone access. In order to identify potentially-eligible patients, we will request a waiver of informed consent, to access clinical diagnostic and pharmacy data. These data will be obtained for VA patients from the Corporate Data Warehouse, which will be accessed and analyzed within the secure user-restricted VINCI study site workspace.

Recruitment: **Clinicians:** PCPs and PACT nurses will be recruited through email, discussions at practice meetings (the PI or a member of the research team will make a presentation during a weekly staff meeting and/or during the monthly meeting for all PCPs), and direct contact by the investigators. **Patients:** We will ask participating PCPs for permission to recruit patients. Using data from the electronic medical record, we will identify patients at the VAPORHCS who potentially meet our inclusion/exclusion criteria. Consistent with the VAPORHCS's policy on recruiting participants for research studies, we will include a signed letter from the clinic manager where the patient receives his/her primary care, or director of primary care. The information sent to patients will include an accompanying letter from the research team, which will describe the study and invite patients to participate in a telephone screening session. Patients will be asked to return enclosed addressed and stamped letters, or to call our research office telephone number if interested in being screened.

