During the screening telephone call, the study research assistant will provide a brief overview of the study purpose (including clear statements that participation involves research and participation does not provide clinical treatment), review inclusion/exclusion criteria, describe what participation in the study would entail, and schedule participants for a study appointment session. If the patient is interested in participating and eligible, the patient will be scheduled for a baseline assessment (participants will also receive reminder phone calls and/or letters prior to their scheduled appointment). To enhance the likelihood of participants attending the study evaluation session, we will offer a \$50 payment in compensation for time and/or travel to attend the research visit. The baseline assessment and all follow-up evaluations will be conducted either in person or via telephone.

During the telephone screening visit, if the participant is ineligible, but is interested in receiving additional clinical services, s/he will be referred to the study PI to contact for information about relevant clinical resources.

During the assessment sessions, the research assistant will provide another overview of study participation, administer informed consent and HIPAA authorization, and instruct the participant to complete study measures.

Follow-up: In addition to the baseline assessment, all participants will complete follow-up assessments every 6 months. During these research visits, participants will complete all study measures (described below). Research visits must be completed within 1 month of the scheduled follow-ups (i.e., the 6-month follow-up must be completed between 5-7 months from baseline and the 12 month follow-up must be completed between 11-13 months from baseline).

Randomization: We will randomize by PCP; patients will be assigned to intervention or control based on randomization of their PCP and PACT nurse. At the VAPORHCS, each PACT nurse is assigned to a single PCP and each PCP has one PACT nurse. Thus, contamination effects by PACT nurses working with a PCP assigned to the control condition will not be a concern.

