We will randomize dyads of PCPs and PACT nurses to receive ISOT versus control. We will initially recruit PCPs to participate. Of the PCPs who choose to enroll, we will then attempt to recruit the PACT nurse who is assigned with that PCP (if the PACT nurse chooses not to participate, the consenting PCP will remain eligible). We will randomly assign consenting PCPs and their PACT nurse (if they choose to participate) to receive ISOT versus control after stratifying by PCP type of training (physician versus nurse practitioner/physician assistant) and proportion of patients in PCP's panel receiving opioid prescriptions (high vs low, based on median eligible clinician population). Using a permuted block randomization and maximizing the number of PCPs (clusters) should prevent major uneven distribution of caseload size and unmeasured confounders across the arms and increase precision.⁷² The statistician will perform the randomization prior to patient recruitment. Research assistants will be blind to intervention status of patients and clinicians.

ISOT Team and Training: ISOT is a multifaceted intervention. The individual components of ISOT have been adapted from recommendations made as part of clinical practice guidelines^{11,16}, our preliminary studies, and prior experience in conducting multifaceted intervention studies in primary care.^{48,51} The unique aspect of this intervention is its integration of different treatment recommendations into a single package. This method of treatment development and adaptation is similar to other effective multifaceted interventions.⁷³

A research nurse care manager (NCM) will be hired to participate in this study. The NCM will be employed full-time. S/he will have clinical training as a registered nurse (R.N.) and have a clinical background in chronic disease management and outpatient treatment. The individual will receive extensive training in chronic pain management, prescription opioid safety, and research procedures.

ISOT Intervention Components

Clinician Education and Activation:

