- a. [name] (Co-Investigator) who has expertise in chronic pain treatment, screening for prescription opioid adherence, and patient-centered care, will conduct the interactive workshop for PCPs and PACT nurses. She has experience providing trainings on this topic. Workshop goals will be designed to optimize clinician interactions via education and activation, while providing system support. We will educate clinicians about prescription opioid adherence monitoring, screening for adverse effects, and enhancing patient-centered care, with a focus on enhancing shared decision making.^{74,75} Clinical recommendations for modifying care in instances of opioid misuse/abuse will be based on our pilot work.¹⁴ The workshop will include brief lecture, demonstration, and participatory skill development. The workshop will be conducted one time, during normal business hours, at the VA Portland Health Care System main campus. The session will be video-recorded. Clinicians who wish to participate in the study, but are not able to attend the in-person session, may view the recording.
- b. The NCM will meet with each PCP and PACT nurse to discuss the intervention, identify attitudes about screening for prescription opioid adherence, and best practices for communicating about these topics.
- c. The primary care pain specialist ([name]) and substance abuse specialist ([name]) will provide consultation to [name] in the development of the training workshop and help facilitate role-play components of the training. They will also consult with the NCM throughout

the intervention as needed.

- d. The NCM will monitor medical records for all enrolled participants to examine potential opioid non-adherence behaviors (e.g., lost prescriptions, early refills, multiple providers, seeking opioids from the ER). For patients with prescription opioid abuse, the NCM will offer decision support to PCPs about treatment options. The NCM will also follow-up to ensure successful implementation of changes in the treatment plan.

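### Patients are recruited after their PCP is randomised, and the plan does not fix PCP permission or the candidate list before allocation

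*Combined protocol and SAP*

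**What the plan says.** The Randomization section makes the PCP, with the PACT nurse, the unit of allocation: "patients will be assigned to intervention or control based on randomization of their PCP and PACT nurse". It then fixes the order of events: "The statistician will perform the randomization prior to patient recruitment".

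Patient entry is described under Recruitment. It begins with the PCP: "We will ask participating PCPs for permission to recruit patients". The research team then finds candidates itself: "Using data from the electronic medical record, we will identify patients at the VAPORHCS who potentially meet our inclusion/exclusion criteria". Invitations carry a letter from the clinic manager or the director of primary care, and patients opt in: "Patients will be asked to return enclosed addressed and stamped letters, or to call our research office telephone number if interested in being screened". At the assessment session the research assistant will "administer informed consent and HIPAA authorization", and the baseline measures follow. The Inclusion Criteria require a current opioid prescription.

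On blinding, the Randomization section says: "Research assistants will be blind to intervention status of patients and clinicians". Study Measures adds that staff collecting outcomes are blind. PCPs and patients are not described as blind. Under the ISOT clinician components, item b says: "The NCM will meet with each PCP and PACT nurse to discuss the intervention". No date is given for that meeting.

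The Aim 1 model adjusts for baseline COMM, age, sex, depressive symptoms, SUD history, pain severity and the two stratification variables.

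**The concern.** In a cluster trial that enrols individuals after allocation, randomisation makes the clusters comparable in expectation. It does not do this for the patients who later enter. If someone who knows the arm can influence who enters, the arms can differ before any outcome is measured.

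Two routes are open here. One is permission, whose timing and form (general or patient by patient) are not stated. The other is prescribing: the PCP decides whether a patient holds a current opioid prescription, and so whether that patient qualifies.

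The Randomization section relies on permuted blocks and many clusters to prevent imbalance in unmeasured confounders. Blocking acts on PCPs and cannot balance which of their patients enrol. Covariate adjustment removes only differences that the covariates capture. PCPs would plausibly judge patients on chart-visible behaviour such as lost prescriptions or early refills, which is not among the covariates. If ISOT PCPs held back difficult patients, the bias would favour ISOT on COMM.

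**Working it through.** **Sequence.** The document gives or implies this order: PCP consent; randomisation; patient recruitment (PCP permission, record search, letters, opt-in); telephone screening; consent and baseline. Randomisation before patient recruitment is explicit. That PCPs know their arm while recruitment runs is an inference. They are not listed as blind, and an ISOT PCP cannot remain unaware once the nurse care manager is working with them, so awareness comes at the latest soon after the first patient enrols.

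**The plan's own figure.** Table 1 gives a detectable difference in COMM change of 2.9 for 32 PCPs per group, 5 patients per PCP and ICC 0.02.
- SE = 8.9 × √(2 × (1 + 4 × 0.02) / 160) = 1.03.
- With df = 2 × (32 − 1) = 62, detectable difference = (2.00 + 0.85) × 1.03 = 2.94. The plan's figure reproduces.

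**Illustrative size of the bias.** From the plan: SD 8.9 and within-subject correlation 0.5. With equal SDs at both times and correlation 0.5, the SD of a score equals the SD of change, so 8.9 can serve for both. Assumed, because the documents give nothing: normal scores, and ISOT PCPs hold back half (f = 0.05) or all (f = 0.10) of their top-decile patients.

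The mean of a normal top decile is 1.755 SD. Removing a fraction f from it shifts the mean by −f × 1.755 / (1 − f):
- f = 0.05: −0.092 SD
- f = 0.10: −0.195 SD

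Write each score as a stable trait plus occasion noise. The trait SD is 8.9 × √0.5 = 6.29. Adjusted bias = follow-up shift − slope × baseline shift, with slope about 0.5.

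1. *Selection on the observed baseline COMM.* Baseline shift is −0.092 × 8.9 = −0.82, or −0.195 × 8.9 = −1.74. The follow-up shift is 0.5 times the baseline shift, so the adjusted bias is about 0 in both cases.
2. *Selection on the stable trait.* Baseline and follow-up both shift by −0.092 × 6.29 = −0.58, or −0.195 × 6.29 = −1.23. Multiplying by (1 − 0.5) gives −0.29 or −0.61. Truncation lowers the pooled slope slightly, and simulation gives about −0.3 or −0.65.
3. *Selection on a PCP impression correlating 0.5 with the trait (assumed).* Half of case 2: about −0.15 or −0.3.

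| Selection on | Half of top decile | All of top decile |
|---|---|---|
| Observed baseline COMM | about 0 | about 0 |
| PCP impression, r = 0.5 | about −0.15 | about −0.3 |
| Stable trait | about −0.3 | about −0.65 |

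**What that does to the test.** With SE 1.03, a residual bias of 0.3 points raises the two-sided 5% error rate to about 6%, and 0.65 points to about 10%. With the smaller SE after baseline adjustment, 1.03 × √(1 − 0.5²) = 0.90, the rates are about 6% and 11%.

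The calculation adjusts for baseline COMM only. The other planned covariates could reduce the bias further. The prescribing route is not quantified.

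**The case against.** The strongest reply is that the plan leaves PCPs little room to choose. Research staff find patients from records on few, objective criteria. The letters do not come from the PCP, patients opt in themselves, and blinded assistants screen and consent them. PCPs would not see the research COMM score. The model adjusts for more than baseline COMM. The Background also argues that clinicians predict opioid abuse poorly, so accurate removal of a top decile is unlikely. All of this stands, and it is why the illustrated bias is small.

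Three stronger readings are tempting, and the document does not support them.
- A reader might infer that PCPs, knowing their arm, vet patients one by one. No veto is described. The permission sentence comes before patient identification, which fits a general permission at least as well.
- A reader might set baseline shifts of 0.8 to 1.7 points against the detectable difference of 2.8 to 3.9. Those shifts are unadjusted baseline differences. The detectable difference concerns change, and the planned model adjusts for baseline COMM, so the comparison is not valid.
- A reader might infer that baseline already carries some of the ISOT effect. The registry and record monitoring cover enrolled patients, the patient appointment is for ISOT patients, and both arms attend the workshop. Only a PCP meeting of unstated date could come before baseline.

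The cover page also refers the reader to a publication for the final protocol and recruitment outcomes. The gap is therefore in this document, and the practice followed may have been tighter. What the reply does not supply is a statement that permission, the list or PCP awareness is protected from allocation.

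**Conclusion.** The point holds as a gap in sequence. Randomisation precedes patient recruitment, PCP permission is part of recruitment, eligibility depends on prescribing, and nothing in this document shields these steps from the PCP's knowledge of arm. The arms can differ at entry; the document does not show that they will.

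Under the assumptions above, the bias in the adjusted COMM difference lies between about 0 and −0.65 points, which could raise the false-positive rate to roughly 10 or 11% at the extreme. These sizes rest on an assumed pattern of withholding for which the documents give no evidence. The case for acting is that the protection is cheap, not that large bias is likely.

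**What to change.** 1. Obtain blanket permission to recruit from each PCP at PCP consent, before randomisation, and state that there is no patient-by-patient veto afterwards.
2. Extract the candidate list from the data warehouse before randomisation and invite patients from it in random order. Still confirm the existing eligibility criteria at screening, and record by arm any listed patients who became ineligible after allocation.

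The second part of item 2 matters because a fixed list cannot stop prescribing from changing after allocation; it makes such losses visible.

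The cost is protocol wording and an earlier data pull. Stratifying on the proportion of each panel receiving opioids already requires panel-level opioid data before randomisation. The downside is that patients who start chronic opioid therapy after the list date cannot be invited, so the pool shrinks by an amount the documents do not let us quantify. If blanket permission was in fact taken at PCP consent, one sentence saying so settles that part.
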